9.6.2 Timings of assessment during follow-up

Table 7 Timing of cohort enrollment, interviews, medical record requests and review*

	Anytime in Pregnancy	20-22 weeks' gestation*	32-34 weeks' gestation	0-6 weeks post-delivery	0-12 months post-delivery
Contact / Referral	√				
Enrollment and Consent	√				
Intake Interview	√				
Interim Interview I		√			
Interim Interview II			√		
Outcome Interview				√	
Medical Record Release Forms Sent for Signature				√	√

*A participant may have anywhere from 1-3 interviews during pregnancy, with a minimum of 4 weeks between interviews. If a participant enrolls at 18 weeks, the 20 week interview will be scheduled at 22 weeks. If a participant enrolls between 19 weeks and 30 weeks, the next scheduled interview will be 32 weeks. If a participant enrolls at 30 weeks, the 32 week interview will be scheduled at 34 weeks. If a participant enrolls after 30 weeks, no additional interviews will be scheduled during pregnancy.

9.7 Statistical analysis

9.7.1 Main analysis

A detailed Statistical Analysis Plan (SAP) will be prepared and finalized prior to the submission of the first interim report.

Primary Endpoint:

The primary endpoint will be major structural defects among live born infants.

The primary comparison will be between the first-trimester benralizumab-exposed group and the disease cohort receiving asthma treatment anytime in pregnancy.

Secondary comparisons for major structural birth defects will be conducted within the subgroup of pregnancies ending in live birth, spontaneous abortion, stillbirth or elective termination, excluding lost-to-follow-up, comparing first-trimester benralizumab-exposed to the treated disease cohort.

Additional secondary comparisons will be made between the first-trimester benralizumab-exposed group and the treated asthma and non-asthmatic cohort, and between the treated asthma and non-asthmatic cohorts. Further details will be specified in the SAP.

Secondary Endpoints:

Preterm Delivery: After exclusion of twins or higher order multiples, the proportion of pregnancies ending in live birth <37 weeks' gestation will be compared between the benralizumab group enrolled and exposed anytime in pregnancy prior to 37.0 weeks' gestation and the treated diseased and non-diseased cohorts enrolled prior to 37.0 weeks' gestation.

Small for Gestational Age Infants: After exclusion of twins or higher order multiples, the proportion of pregnancies ending in a live born infant \leq 10th centile of birth weight, length and/or head circumference will be compared between the benralizumab group exposed anytime in pregnancy and the treated diseased and non-diseased cohorts.

Spontaneous Abortion: For those women in all three cohorts who enrolled in the study prior to 20.0 weeks' gestation, the proportion of pregnancies ending in spontaneous abortion accounting for left truncation will be compared between those in the benralizumab group enrolled and exposed any time in pregnancy prior to 20.0 weeks' gestation and those in the treated diseased and non-diseased cohorts.

Stillbirth: The proportion of pregnancies ending in stillbirth will be compared between those in the benralizumab-exposed group and those in the treated diseased and non-diseased cohorts.

Elective Termination: The proportion of pregnancies ending in elective termination will be compared between the benralizumab exposed group enrolled prior to 20.0 weeks' gestation, and the diseased and non-diseased cohorts enrolled prior to 20.0 weeks' gestation.

Small for Age Postnatal Growth: After exclusion of twins or higher order multiples, the proportion of pregnancies ending in a live born infant \leq 10th centile of postnatal weight, length and/or head circumference will be compared between the benralizumab group exposed anytime in pregnancy and the treated diseased and non-diseased cohorts.

Statistical methods:

Descriptive tables will be prepared for characteristics of each of the cohorts in each interim and final report displaying n, means, standard deviations, minimums and maximums or proportions and percentages.

For the primary endpoint of major structural defects, and for the secondary endpoints of small for gestational age infants, postnatal growth and elective termination, un-adjusted relative risk estimates will be presented together with exact two-sided 95% and 80% confidence intervals.

For the secondary endpoints of preterm delivery, spontaneous abortion, and stillbirth, survival methods will be used (Kaplan Meier) to estimate crude rates and confidence intervals accounting for gestational timing of enrollment in the study.

Adjusted analyses producing relative risks and 95% and 80% confidence intervals or hazard ratios and 95% and 80% confidence intervals, where numbers permit, will be conducted. A minimum of 30 events in the overall analysis sample is required for adjusted analysis for those outcomes assessed with logistic regression. A minimum of 20 events in the overall analysis sample is required for adjusted analysis for those outcomes assessed with Cox Proportional Hazards.

Confounders will be considered for each adjusted analysis separately, using the method of change in estimate of the effect of exposure to benralizumab by 10% or more. If one confounder is identified, direct adjustment will be performed. However, given the expected low frequency of events in a study of this size, if two or more confounders are identified in any given analysis, a propensity score approach for adjustment will be considered. Appropriateness of models will be assessed graphically and by standard statistical methods.

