Data sources: Data will be collected using maternal interview(s), medical records (obstetric, delivery hospital, pediatric, allergist and/or other specialty provider), and pregnancy exposure diary. Maternal interview data will be recorded on hard copy forms, and medical record abstraction data will be recorded on electronic forms, and these records will be retained by OTIS. Maternal interview forms are considered the primary data sources for the study. Data from these forms will be extracted and entered into a customized OTIS study database located in the OTIS Research Center and developed specifically for the OTIS studies.

Study size: The target sample size for the study is 200 women in the benralizumab-exposed cohort; 300 women in the treated diseased cohort; and 300 women in the non-diseased cohort.

Statistical method: Demographic and baseline characteristics will be compared between the cohorts. The primary analysis will be a comparison of the prevalence rate of major structural defects in live born infants between the benralizumab-exposed cohort and the treated disease cohort. Where numbers permit, multivariable analyses will be conducted to determine the

relationship of benralizumab with the primary outcome of major structural birth defects, and separately for each of the secondary outcomes of small for gestational age, preterm delivery, spontaneous abortion, stillbirth, elective termination and small for age postnatal growth. There will be no formal hypothesis testing, rather point estimates of the rate ratios along with confidence intervals will be presented.

Milestones: The study is planned for 7 years from start of enrollment (first patient in (FPI) to study completion). There will be 5 years of active recruitment, with an interim report reviewed by the Scientific Advisory Committee each year. The final report with statistical analysis according to the SAP will be prepared at the end of the study.

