9.3.2 Outcome definitions

- **Major Structural Birth Defects:** a major structural defect is defined and classified using the CDC coding manual (CDC, 2007), as reported by the mother and validated through the medical record. The CDC coding manual is utilized to classify defects reported through the ongoing population-based Metropolitan Atlanta Congenital Defects Program (MACDP) and is based on agreed-upon criteria by CDC investigators for major structural defects regardless of etiology. Infant medical records are abstracted by the data coordinator, and reviewed by the study manager. Final validation of the classification of

all major birth defects reported in the study will be conducted by the OTIS Co-Investigator with expertise in the diagnosis of birth defects.

- **Preterm Delivery:** preterm delivery is defined as a spontaneous or induced delivery at <37 gestational weeks, reported by the mother and validated through the medical record. Please refer to Section 9.3.1 for further description of the method for defining gestational age and therefore preterm birth.
- **Small for Gestational Age (SGA) Infants:** Live born infants who are \leq 10th centile on birth weight, length and/or head circumference for infant sex and gestational age will be considered small for gestational age. The U.S. Centers for Disease Control and Prevention (NCHS) growth charts will be used for full term infants, and preterm growth charts will be used for preterm infants (Lubchenco, 1966). The outcomes of birth weight, length and head circumference are reported by the mother and validated through the medical record.
- **Spontaneous Abortion:** Spontaneous abortion is defined as spontaneous pregnancy loss prior to 20.0 weeks' gestation. In this study, since women enroll after recognition of pregnancy, spontaneous abortions are only identified after enrollment in clinically recognized pregnancies. This outcome is reported by the mother and validated through the medical record.
- **Stillbirth:** Stillbirth is defined as a fetal death that occurs \geq 20 weeks' gestation. This outcome is reported by the mother and validated through the medical record.
- **Elective Termination:** Elective termination is defined as deliberate interruption of pregnancy by surgical or medical means.

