- **Small for Age Postnatal Growth:** Postnatal growth is measured at approximately 1 year of age among live born infants and age and sex specific percentiles assigned using standard U.S. growth curves. Weight, length and/or head circumference \leq 10th centile will be considered small for age. The outcomes of postnatal weight, length and head circumference are collected from pediatric records.

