				1.5	0.76	0.47	0.18	0.02
				2	0.96	0.83	0.49	0.08
SGA infant	10%	200/300	180/270	1	0.26	0.07	0.01	0.00
				1.2	0.49	0.19	0.03	0.00
				1.5	0.81	0.48	0.13	0.00
				2	0.99	0.88	0.50	0.05

Numbers in Table 5 are based on 90% of enrolled pregnancies ending in live birth with completed outcome. The effect size for all birth defects among live births is based on a prevalence of 3% in the asthmatic comparison group. The effect size for preterm birth is

based on a prevalence of 7% in the asthmatic comparison group (Bakhireva, 2008). The effect size for small for gestational age infants (SGA) is based on a prevalence of 10% in the asthmatic comparison group. Simulations were done using R to estimate the probabilities presented in Table 5.

It is projected, based on experience with the EXPECT registry that almost all benralizumab-exposed participants will have received at least one dose of the medication in the period of time from eight weeks prior to LMP to the end of the trimester and will be eligible for analysis of major structural birth defects. It is also expected that the majority of study participants will enroll in the study upon recognition of pregnancy in the first trimester; however, some will enroll after 20 weeks' gestation and therefore will not be included in the analysis of spontaneous abortion.

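### Birth size and one-year growth are measured, but 9.7.1 compares cohorts only on a 10th-centile yes/no composite, so moderate growth shifts are estimated less precisely than the data allow

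*Protocol*

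**What the plan says.** Protocol 9.3.2 collects the underlying measurements. For birth: "The outcomes of birth weight, length and head circumference are reported by the mother and validated through the medical record". For one year: "The outcomes of postnatal weight, length and head circumference are collected from pediatric records", with age- and sex-specific percentiles assigned.

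Both outcomes are then cut. An infant at or below the "10th centile on birth weight, length and/or head circumference for infant sex and gestational age will be considered small for gestational age". At one year, weight, length and/or head circumference at or below the "10th centile will be considered small for age". Each endpoint is therefore a composite: falling below the cut on any one of three measures counts.

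Section 9.7.1 compares the cohorts on the proportion at or below the cut, singletons only. For the crude analysis, "for the secondary endpoints of small for gestational age infants, postnatal growth and elective termination, un-adjusted relative risk estimates will be presented" with exact two-sided 95% and 80% intervals. The adjusted analyses give relative risks or hazard ratios. The means and standard deviations in the same section describe cohort characteristics. Section 9.7.2 adds no measured-scale growth analysis.

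For planning, 9.5 states: "The effect size for small for gestational age infants (SGA) is based on a prevalence of 10% in the asthmatic comparison group", and "Numbers in Table 5 are based on 90% of enrolled pregnancies ending in live birth with completed outcome".

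**The concern.** Cutting a measurement at a low centile discards information on how far each infant lies from the cut. In a small sample of fixed size this widens the uncertainty about a drug effect that moves the whole growth distribution. Section 9.5 says that point estimates and intervals will be used to judge potential risk, so precision decides what the study can say. The measurements are already in hand and no reason is given for using the cut alone. The composite also cannot show which of weight, length or head circumference moved.

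At stake is the reading of two secondary outcomes. A moderate shift in growth could be reported as an interval that includes no effect when the same infants would have supported a clearer statement. The primary outcome is not affected.

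**Working it through.** **Inputs from the protocol.** Enrolment targets of 200 exposed and 300 treated asthma (Abstract, 9.5); 90% with live birth and complete outcome, giving 180 and 270; SGA prevalence 10% in the comparator; true RR 1.2, 1.5 and 2 (9.5, Table 5); two-sided 95% and 80% intervals (9.7.1).

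**Assumptions not in the protocol.** Normal z-scores with equal SDs, shifted uniformly by exposure; for the composite, three measures with equal pairwise correlation 0.5 or 0.7, all shifted by the same amount.

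**Step 1: reproduce Table 5.** I enumerated two independent binomials, Bin(180, 0.10·RR) and Bin(270, 0.10), and took the probability that the observed RR exceeds X. At true RR 1.5 this gives 0.803, 0.472, 0.129 and 0.004 for X = 1.2, 1.5, 2 and 3. Table 5 states 0.81, 0.48, 0.13 and 0.00. All 16 SGA cells agree within 0.01.

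**Step 2: one measure, 10% below the cut.** The shift is d = Φ⁻¹(0.10·RR) − Φ⁻¹(0.10). At RR 1.5, d = −1.036 + 1.282 = 0.245 SD (from unrounded values).

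Measured scale: P(95% interval lies above zero) = 1 − Φ(1.96 − d·√(n₁n₀/(n₁+n₀))). Here √(180·270/450) = √108 = 10.39, so d·10.39 = 2.55 and the probability is Φ(0.59) = 72%.

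Yes/no scale: the same question for the relative risk, with an approximate interval. Exact intervals tend to be wider, so these figures are if anything optimistic.

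| True RR | Shift (SD) | 95% CI, yes/no | 95% CI, z-score | 80% CI, yes/no | 80% CI, z-score |
|---|---|---|---|---|---|
| 1.2 | 0.107 | 10% | 20% | 27% | 43% |
| 1.5 | 0.245 | 36% | 72% | 62% | 90% |
| 2 | 0.440 | 84% | 99.5% | 95% | 99.9% |

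**Step 3: information kept by the cut.** Efficiency is φ(z_p)²/[p(1−p)]. At p = 0.10 it is 0.34; at 0.20, 0.49; at 0.25, 0.54.

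**Step 4: the and/or composite.** I simulated three correlated z-scores and found the common shift that multiplies the composite risk by RR. I then compared the composite's relative risk with the mean difference in a single z-score (95% intervals, 180/270).

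| Composite prevalence | Correlation | RR 1.5: shift (SD) | RR 1.5: yes/no | RR 1.5: one z-score | RR 2: yes/no | RR 2: one z-score |
|---|---|---|---|---|---|---|
| 10% (the protocol's figure) | 0.5 | 0.220 | 36% | 63% | 84% | 98% |
| 10% (the protocol's figure) | 0.7 | 0.231 | 36% | 67% | 84% | 99% |
| 22% (each measure cut at 10%) | 0.5 | 0.295 | 73.0% | 86.5% | 99.8% | over 99.9% |
| 19% (each measure cut at 10%) | 0.7 | 0.289 | 64.7% | 85.2% | 99.3% | over 99.9% |

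**Step 5: one-year growth, an extension only.** Table 5 has no postnatal row and the protocol gives no record rate. If 80% have records (assumed; 0.8·180 = 144 and 0.8·270 = 216), the single-measure calculation gives 30% against 62% at RR 1.5, and 76% against 98% at RR 2.

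**The case against.** The outcomes are named as conditions, small for gestational age and small for age, and a relative risk is a proper estimate for a condition. That stands, and is why the ratios should be kept. It does not explain why the measurements are used in no other comparison.

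A supplementary z-score model is often left to the SAP, and the unseen SAP may contain one. That is fair. The point here is that 9.7.1 itself states the scale, the effect measure and the intervals for these endpoints, and the stated choice can be improved.

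The study does no formal testing, and version 2.0 moved away from statistical significance. The percentages above should therefore be read as a way of expressing interval precision, not as power for a planned test. On the protocol's own yardstick the yes/no endpoint is not uninformative: Table 5 gives an 81% chance of an observed SGA RR above 1.2 when the truth is 1.5.

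Three stronger readings are tempting and are not supported:

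- **That growth effects across the whole Table 5 range would be missed.** At RR 2 the yes/no interval for birth size already excludes 1 in about 84% of studies or more. At RR 1.2 both scales usually fail. The single-measure 36% against 72% also ignores the composite.
- **That the 30-event minimum for logistic regression threatens adjusted growth results.** At 10% of 450 infants, 45 events are expected and the chance of fewer than 30 is 0.5%. At 360 infants it is 12%. For SGA at the planned size the rule almost never binds.
- **That the one-year figures come from the protocol.** They rest on an assumed record rate and on effect sizes that Table 5 does not apply to postnatal growth.

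**Conclusion.** The point holds as a loss of precision for moderate shifts, not as an error in the endpoints. At RR 1.5 with 180/270 infants, the chance that the 95% interval excludes no effect is 36% on the yes/no scale against 63–72% for one z-score, if the composite has the protocol's 10% prevalence. It is about 65–73% against 86% if the composite is nearer 19–22%. At RR 2 the gain is about 14–15 points at 10% prevalence and essentially nil near 20%.

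These figures rest on normal z-scores and a uniform shift, with the composite rows adding assumed correlations of 0.5–0.7 and an equal shift in all three measures. An effect confined to the lower tail would not show the gain and could favour the cut. The mean difference therefore belongs beside the ratio, not in its place.

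**What to change.** Keep the 10th-centile relative risks as the endpoints. Add to 9.7.1, as a supportive analysis in singletons, the difference in mean sex- and age-specific z-score (for gestational age at birth) for each of weight, length and head circumference, at birth and at about one year, versus each comparison cohort. Estimate it by linear regression with 95% and 80% intervals, adjusted under the plan's existing confounder rules. Where the growth charts give only centiles, regress the raw measurement on exposure, sex and gestational age (age at measurement for the one-year data). State that the mean difference is read together with the ratio.

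The cost is a few lines of text and a few tables, with no new data or participants. The downside is six more estimates per comparison (three measures at two times) to interpret, and a mean shift may not reflect an effect limited to the smallest infants.

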9.2 Setting

The study population consists of three cohorts of pregnant women (See Section 9.5 for sample size).

Participants will be recruited into the three cohorts concurrently, on the basis of the following inclusion/exclusion criteria:

Cohort 1: Benralizumab-Exposed

Inclusion Criteria:

- Currently pregnant women diagnosed with asthma who contact the OTIS Research Center and who have been exposed to benralizumab for any number of days, at any dose, and at

any time from 8 weeks before the first day of LMP up to and including the end of pregnancy.

- Eligible participants will be currently pregnant women who agree to the conditions and requirements of the study including the interview schedule and release of medical records.

Exclusion Criteria:

- Women who have had exposure to another biologic, used for any indication, anytime during pregnancy or within 8 weeks of LMP.
- Women will not be eligible for Cohort 1 if they first contact the OTIS Research Center after prenatal diagnosis of a major structural birth defect.
- Retrospective cases (outcome of pregnancy known prior to enrollment).
- Women who have enrolled in the current study with a previous pregnancy.

Cohort 2: Treated Diseased Comparison

Inclusion Criteria:

- Currently pregnant women diagnosed with asthma and exposed to asthma medications for any number of days, at any dose, and at any time from LMP up to the date of enrollment, who contact the OTIS Research Center but who were not exposed to benralizumab during pregnancy or within 8 weeks prior to LMP.
- Eligible participants will be currently pregnant women who agree to the conditions and requirements of the study including the interview schedule and release of medical records.

Exclusion Criteria:

- Women with exposure to benralizumab any time during pregnancy or within 8 weeks prior to LMP.
- Women will not be eligible for Cohort 2 if they first come in contact with the OTIS Research Center after prenatal diagnosis of a major structural birth defect.
- Retrospective cases (outcome of pregnancy known prior to enrollment).
- Women who have enrolled in the current study with a previous pregnancy.

Cohort 3: Non-Asthmatic Comparison

Inclusion Criteria:

- Currently pregnant women who contact the OTIS Research Center.
- Eligible women may potentially have been exposed to non-teratogenic agents during this pregnancy.

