9.3 Variables

9.3.1 Exposure definitions

Benralizumab-exposed cohort: Exposure is defined as any dose of benralizumab for any length of time from 8 weeks prior to LMP through the end of pregnancy, as reported by the mother and validated through medical record review. The 8-week cut-off prior to LMP is based upon the terminal half-life of benralizumab of approximately 15 days (clearance of benralizumab is based on five half-lives).

Exposure is defined as yes/no in the first trimester of pregnancy for major structural birth defects as the primary outcome. For this study, first trimester exposure is defined as any dose between 8 weeks prior to LMP and 13 weeks after LMP. However, exposure to benralizumab in the second (>13 weeks through 26 weeks after LMP) and third trimester (>26 weeks after LMP) will be considered for those selected major birth defects that are potentially biologically plausibly related to later pregnancy exposures, e.g., craniosynostosis. For spontaneous abortion, exposure is defined as yes/no in the first 20 weeks of gestation, and for the other secondary outcomes, exposure is defined as yes/no anytime in pregnancy.

Gestational age is determined by an algorithm using best available information. If LMP and cycle length is known, and ultrasound measures of dating are not discrepant according to standard conventions depending on the timing of the ultrasound, the menstrual period dating will be used to calculate gestational age. If the menstrual period dating is uncertain or unknown, and an ultrasound is available, the earliest (and therefore more precise) available dating ultrasound will be used. In the event of absence of any information on dating, the delivery record best estimate of gestational age will be used.

In exploratory analyses, duration of benralizumab use in pregnancy, specific gestational timing, and dose of benralizumab will be explored. In the asthmatic comparison group, duration of other asthma medications use in pregnancy, specific gestational timing, and doses will be explored.

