Preterm Delivery	Pregnancies enrolled prior to 37.0 weeks' gestation and ending in at least one live born infant. Excludes twins or higher order multiples due to inherent higher risk of preterm birth in multiples. Exposure can occur any time in pregnancy prior to the event.
Small for Gestational Age Infants	Pregnancies ending in at least one live born infant; excluding twins or higher order multiples due to the inherent higher risk of reduced birth size in multiples. Exposure can occur any time in pregnancy prior to the event.
Still birth	All pregnancies, excluding lost-to-follow-up. Exposure can occur any time in pregnancy prior to the event.
Elective Termination	All pregnancies, excluding lost-to-follow-up. Exposure can occur anytime in pregnancy prior to the event.
Postnatal Growth	Pregnancies ending in at least one live born infant with pediatric growth records available at approximately 1 year of age. Multiples are excluded. Exposure can occur anytime in pregnancy.

Coding of outcomes is performed by the study staff using the definitions provided in the protocol. Interview, diary, and examination data will be recorded on hardcopies of forms, medical records and medical record abstraction forms may be recorded on hardcopies or electronically; these records will be retained in the Coordinating Center. Data from all forms will be extracted and entered into a customized database located in the Coordinating Center. The data will be extracted and entered by trained study personnel with extensive experience with this type of information. Entries will be periodically reviewed for logical errors, and intake and outcome forms will be validated for data entry accuracy.

The primary source for information collected on demographics and exposures is by maternal interview, as the participant typically provides more accurate information than the medical records, especially in regards to non-prescription medications and any medications not taken as prescribed. Doses, dates, and timing of exposure are confirmed with medical records. If the medication is administered in the office, the medical record is the primary source; if the medication is administered at home and there is a discrepancy between the record and maternal report, the participant is contacted and asked about the discrepancy.

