9.7.2 Exploratory/sensitivity analyses

Exploratory analyses addressing potential effect modifiers such as Asthma Control Test measures of disease symptom control, and measures of asthma exacerbation will be addressed.

In addition, sub-analyses based on length and gestational timing as well as dose of exposure to benralizumab will be performed.

Stratified analyses based on prenatal diagnostic test performed prior to enrollment in the study will be conducted for the primary endpoint. The purpose of this analysis is to address the inherent bias in excluding women at the time of enrollment in the cohort study who have already received prenatal diagnosis of a major structural birth defects, but including women who have already had a normal result or prenatal diagnosis for major structural birth defects prior to enrollment. Therefore, the planned stratified analysis will compare the birth prevalence of major structural birth defects among the subset of women enrolled in the cohorts prior to prenatal diagnostic testing to detect structural defects (ultrasound for structure, chorionic villus sampling, amniocentesis), to the birth prevalence of major birth defects among the subset of women enrolled in the cohorts after prenatal diagnostic testing to detect structural defects.

Regarding asthma severity, the measures are only captured after enrollment, and in the exposed group only after being on treatment, so they would typically not be included in the analysis as adjustment factors as they could be mediators. However, descriptive analyses of the balance in cohorts on measures of disease severity are presented. Sub-analyses or

sensitivity analyses within disease severity categories can be performed, depending on the distribution of the covariates. This would be described in detail in the SAP.

Sub-analyses excluding chromosomal or known genetic anomalies (classified by study investigators as having a known genetic etiology) will also be conducted. Details will be provided in the SAP.

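### Benralizumab exposure is a fixed yes/no over a window that stays open after enrolment, so any first dose after enrolment biases spontaneous abortion, and to a lesser extent preterm delivery, towards apparent protection

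*Protocol*

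**What the plan says.** **Cohort entry (section 9.2).** Cohort 1 is women "who have been exposed to benralizumab for any number of days, at any dose", at "any time from 8 weeks before the first day of LMP up to and including the end of pregnancy". The Cohort 2 exclusion reads "Women with exposure to benralizumab any time during pregnancy or within 8 weeks prior to LMP". Both windows run on after enrolment. By contrast, the window for the asthma medication that qualifies a woman for Cohort 2 stops at the date of enrolment.

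**Exposure coding (section 9.3.1).** "For spontaneous abortion, exposure is defined as yes/no in the first 20 weeks of gestation"; "for the other secondary outcomes, exposure is defined as yes/no anytime in pregnancy".

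**Denominators (section 9.6.1, Table 6).** For spontaneous abortion, preterm delivery and stillbirth: "Exposure can occur any time in pregnancy prior to the event".

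**Analysis (section 9.7.1).** For these three outcomes "survival methods will be used (Kaplan Meier) to estimate crude rates and confidence intervals accounting for gestational timing of enrollment in the study". The spontaneous-abortion paragraph also requires allowance for left truncation. It takes benralizumab women who were both enrolled and exposed before 20.0 weeks, without saying which came first. Cox models are foreseen where events suffice. The date of first dose is nowhere an entry time or a time-dependent covariate.

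**Sub-analyses (section 9.7.2).** "sub-analyses based on length and gestational timing as well as dose of exposure to benralizumab will be performed". No method is given.

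**The concern.** Take a treated-asthma woman who enrols at 8 weeks and has her first benralizumab dose at 14 weeks. Her dose falls inside the Cohort 1 window and breaches the Cohort 2 exclusion, and Table 6 accepts it because it precedes any later event. If she is analysed as exposed from enrolment, weeks 8 to 14 count as exposed time. She had to remain event-free in those six weeks to become exposed at all. Had she miscarried at 12 weeks, the loss would have stayed in Cohort 2. This is immortal time.

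If she is instead dropped from Cohort 2, the comparator loses event-free weeks and keeps its losses, so its hazard rises. The protocol does not say which treatment applies, but both make benralizumab look safer. In a study meant to detect harm, that is the unwelcome direction.

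A related risk attaches to length of use. A pregnancy that ends early cannot accumulate late doses, so grouping by total use can confuse long treatment with long pregnancy.

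**Working it through.** **The plan's own figure.** Table 5 is the only quantitative statement about these comparisons. Exact enumeration of two binomials (180 and 270 pregnancies) reproduces all its cells within 0.02. For preterm delivery at 7%, the probability of an observed RR above 1.5 is 0.103 against a printed 0.10 when the true RR is 1, and 0.823 against 0.83 when it is 2. Table 5 is not in question, but it takes no account of when exposure begins.

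**Which women matter.** Delayed entry at enrolment already removes the immortal time of every woman dosed before enrolment. Only women first dosed after enrolment can cause the bias, so their share drives its size.

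**Simulation with no drug effect.** The 7% preterm risk comes from section 9.5. The following are assumptions that the documents do not give:
- spontaneous abortion: 15% cumulative risk over weeks 5-20, hazard falling as exp(-0.2t), enrolment uniform over weeks 6-18;
- preterm delivery: hazard rising over weeks 24-37, enrolment uniform over weeks 6-20 or 6-34;
- late starters' first dose uniform from enrolment to the end of the risk period.

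The estimate is a Mantel-Haenszel risk-set rate ratio with delayed entry at enrolment. The true value is 1.00.

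| Approximate share of Cohort 1 first dosed after enrolment | 0% | 5% | 10% | 20% | 40% |
|---|---|---|---|---|---|
| Spontaneous abortion, fixed yes/no | 0.995 | 0.962 | 0.932 | 0.868 | 0.737 |
| Preterm, enrolment to week 20 | 1.005 | 0.998 | 0.991 | 0.976 | 0.946 |
| Preterm, enrolment to week 34 | 0.996 | 0.985 | 0.975 | 0.953 | 0.910 |

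The 0% column shows simulation error of about 0.005. With exposed time starting at the later of enrolment and first dose, every scenario returns 0.995-1.006.

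**The other reading: late starters dropped from Cohort 2.** Assume 10% spontaneous abortion over weeks 6-20, enrolment uniform over weeks 6-14 and no drug effect. Excluding about 5%, 10% or 20% of Cohort 2 gives ratios of about 0.97, 0.93 and 0.86. Censoring those women at first dose instead gives about 1.00.

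**Size against precision.** Assume 10% spontaneous abortion among 200 and 300 women, which is 20 and 30 events. Then SE(log HR) = sqrt(1/20 + 1/30) = 0.29, and the 95% interval extends by a factor of exp(1.96 x 0.29), about 1.8, either way. A shift to 0.96 is |ln 0.96|/0.29 = 0.14 SE. A shift to 0.87 is 0.139/0.29 = 0.48 SE.

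**Length of use, if total doses were used as a group.** Assume doses every 8 weeks (the maintenance interval described in section 7), a random phase and no drug effect.
- Preterm, at least 6 versus fewer than 6 doses: RR 0.084, 0.237 and 0.318 when 100%, 50% and 20% of women continue treatment.
- Preterm, at least 5 versus fewer than 5: 0.818 and 0.883 (50% and 20% continuing).
- Preterm, at least 4 versus fewer than 4: 1.019 and 1.003.
- Spontaneous abortion, at least 3 versus fewer than 3: 0.16 and 0.229.

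The distortion is large when the cut-point is reached only late in the risk period, and absent when it is reached before that period starts.

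**The case against.** The strongest reply is that cohorts are in effect set at enrolment. Cohort 1 is described in the perfect tense ("who have been exposed to benralizumab for any number of days, at any dose"), and section 9.7.2 says severity in the exposed group is measured only once women are on treatment. Section 9.5 expects almost all exposed women to have had a dose by the end of the trimester, and section 9.9 reports that exposures in the omalizumab registry were mostly confined to the first trimester. Late starters should then be few, and the bias small against the precision available.

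Much of this stands. A reader might infer that the survival analyses are certain to count unexposed weeks as exposed. The documents do not support that: it needs women who enter Cohort 1 with a first dose after enrolment, and section 9.2 can be read as not admitting them. What the reply does not settle is the Cohort 2 exclusion, which on any reading extends past enrolment. Nor does a dose by the end of the trimester mean a dose before enrolment: a woman who enrols at 8 weeks and is first dosed at 12 weeks fits the projection and still brings four immortal weeks.

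A reader might also infer that the length-of-use results will show false protection. One can construct a preterm ratio of about 0.07 by putting every preterm birth at week 34 and every term birth at week 39 among continuous users. Section 9.7.2 fixes no grouping, cut-point or model, so this is a risk to guard against and does not follow from any stated analysis.

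Deferral to the SAP answers the length-of-use point in part. It does not answer the main one, because the protocol itself already fixes the yes/no definition and the enrolment-only correction.

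**Conclusion.** The point holds in a limited form. The exposure definition, the open window and the correction for enrolment alone together leave any first dose after enrolment wrongly handled, and both possible treatments of such women err towards protection. At 0-5% late starters the spontaneous-abortion HR is about 0.95-1.00 and the preterm HR about 0.99-1.00, which is negligible beside the expected confidence interval. For spontaneous abortion it becomes material at roughly 10-20% or more (about 0.93 to 0.87). Preterm delivery is less affected because most of its risk falls late. Stillbirth follows the same logic, but its size was not computed.

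The sizes rest on assumed enrolment, hazard and starting patterns; the direction does not. The length-of-use distortion is conditional on a method that the protocol has not chosen. The change is worth making because it is cheap and the error runs the wrong way for a safety study.

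**What to change.** - **Section 9.2:** state that cohort is assigned on exposure up to enrolment, for both the Cohort 1 window and the Cohort 2 exclusion.
- **Section 9.3.1, Table 6 and section 9.7.1:** for spontaneous abortion, stillbirth and preterm delivery, start exposed time at risk at the later of enrolment and first benralizumab dose. Use this entry time in the Kaplan-Meier estimates and time-dependent exposure in the Cox model.
- **Cohort 2 women who start benralizumab:** censor them in Cohort 2 at that dose and count them as exposed from then on. Do not reclassify or exclude them retrospectively.
- **Section 9.7.2:** analyse length and timing with time-dependent cumulative exposure, or by doses received up to a fixed gestational landmark among pregnancies still ongoing at that point.
- **Reporting:** give the number of women first dosed after enrolment, so that the size of the issue is visible.

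The cost is wording and a little programming; dose dates and gestational age are already collected. The downside is that a few women contribute time to both cohorts. The change does not remove confounding by whatever worsening of asthma led to the later start.
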